3.1 Eligibility Criteria

Participants must meet the following criteria on screening examination to be eligible to participate in the study:

- 3.1.1 Participants must have histologically confirmed invasive breast cancer that is metastatic or unresectable locally advanced. Histological documentation of metastatic/recurrent breast cancer is not required if there is unequivocal evidence for recurrence of the breast cancer.
- 3.1.2 Estrogen and/or progesterone receptor positive breast cancer, as determined by pathology from either primary or metastatic site(s). Central confirmation is not required.
- 3.1.3 HER2 negative, defined as 0-1+ by immunohistochemistry or FISH-negative (ratio < 2.2). Central confirmation is not required.
- 3.1.4 Postmenopausal women are eligible. Postmenopausal is defined as any of the following:
- Age > 60 years
 - Age > 45 with intact uterus and amenorrhea for 12 months or more
 - Follicle stimulating hormone (FSH) levels within postmenopausal range according the ranges established by the testing facility
 - Premenopausal women who have been on a GnRH agonist for at least 3 consecutive months prior to study entry are eligible. Women in this group **MUST** remain on the GnRH agonist for the duration of protocol treatment.
 - Status-post bilateral oophorectomy-After adequate healing post surgery.
- 3.1.5 Women and men, age \geq 18 years of age
- 3.1.6 Measurable disease is required. Measurable disease is defined as at least one lesion that can be accurately measured in at least one dimension (longest diameter to be recorded) as \geq 20 mm with conventional techniques or as \geq 10 mm with spiral CT scan. Bone lesions, leptomeningeal disease, ascites, pleural/pericardial effusions, lymphangitis cutis/pulmonis, inflammatory breast disease, abdominal masses identified by physical exam that are not measurable by reproducible imaging techniques, and cystic lesions are all considered non-measurable. See section 10 for details. **As of 4/30/14, the evaluable/non-measurable cohort has been filled and only patients with measurable disease are allowed moving forward. Prior to 4/30/14, up to 20% of patients entered on this trial (i.e. 14 patients) were entered with evaluable but nonmeasurable disease.**

CONFIDENTIAL

This document is confidential. Do not disclose or use except as authorized.

3.1.7 Endocrine resistant breast cancer, defined as either:

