3.1.18 Adequate IV access

3.1.19 Fulvestrant is contraindicated in pregnancy (category D). The effects of ganetespib on the developing human fetus are unknown. For these reasons, women of child-bearing potential and men must agree to use adequate contraception (hormonal or barrier method of birth control; abstinence) prior to study entry and for the duration of study participation. Should a woman become pregnant or suspect she is pregnant while participating in this study, she should inform her treating physician immediately. Premenopausal women who have been on a GnRH agonist for at least 3 consecutive months prior to study entry are eligible. Women in this group **MUST** remain on the GnRH agonist for the duration of protocol treatment. Such patients should be counseled that GnRH agonists alone may not be adequate contraception and that adequate contraception (hormonal or barrier method of birth control; abstinence) prior to study entry and for the duration of study participation should be employed.

3.1.20 Ability to understand and the willingness to sign a written informed consent document.

3.1.21 Patients on therapeutic dose anti-coagulation with warfarin, LMWH, or other anti-coagulants will be allowed to participate in the study. However, the anti-coagulants should be held pre- and post- research biopsy (when applicable) as per institutional standards. The risks of a temporary hold of anti-coagulation should be carefully considered and explained to the patient as part of the informed consent process. If it is not felt to be in the best interest of the patient to have anti-coagulation held, the patient may still enter the study, but should not undergo a research biopsy.

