3.2 Exclusion Criteria

Participants who exhibit any of the following conditions at screening will not be eligible for admission into the study.

CONFIDENTIAL

This document is confidential. Do not disclose or use except as authorized.

- 3.2.1 Prior treatment with an HSP90 inhibitor (e.g. 17-AAG, IPI-504, AUY922, STA-9090 (ganetespib) etc.)
- 3.2.2 Prior treatment with fulvestrant.
- 3.2.3 Participants may not be receiving any other investigational agents.
- 3.2.4 Concurrent treatment with commercial agents or other agents with the intent to treat the participant's malignancy, including endocrine therapy, chemotherapy, and/or targeted therapy, with the exception of bisphosphonates and GnRH agonists, as detailed in Section 3.1.8 and 3.1.10.
- 3.2.5 Untreated or progressive brain metastases. Patients with treated brain metastases not requiring chronic corticosteroids for symptom control are eligible.
- 3.2.6 Pending visceral crisis, in the opinion of the treating investigator.
- 3.2.7 History of allergic reactions attributed to compounds of similar chemical or biologic composition to fulvestrant or ganetespib.
- 3.2.8 Uncontrolled intercurrent illness including, but not limited to ongoing or active infection, or psychiatric illness/social situations that would limit compliance with study requirements.
- 3.2.9 Serious cardiac illness, defined as follows:
- Clinically unstable cardiac disease, including unstable atrial fibrillation, symptomatic bradycardia, unstable congestive heart failure, active myocardial ischemia, or indwelling temporary pacemaker
 - Ventricular tachycardia or a supraventricular tachycardia that requires treatment with a Class Ia antiarrhythmic drug (e.g., quinidine, procainamide, disopyramide) or Class III antiarrhythmic drug (e.g. sotalol, amiodarone, dofetilide). Use of other antiarrhythmic drugs is permissible.
 - Use of medications that have been linked to the occurrence of torsades de pointes (see Appendix I for a list of such medications). Investigators should note that Zofran (ondansetron) has been linked to QTc prolongation and the occurrence of torsades de pointes. Therefore it should not be used in patients being treated with ganetespib. The use of all other serotonin 5 HT3 antagonists is acceptable (e.g., palonsetron, granisetron, tropisetron).
 - Second- or third degree atrioventricular block (AV block) unless treated with a permanent pacemaker.
 - Complete left bundle branch block (LBBB)

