 - History of long QT syndrome or a family member with this condition
- 3.2.10 Corrected QTc > 470 msec. The corrected QTc may be corrected using either Bazett's or Friderica's formula. In general QTcf is the preferred correction method.

CONFIDENTIAL

This document is confidential. Do not disclose or use except as authorized.

- 3.2.11 Pregnant women are excluded from this study because fulvestrant is contraindicated in pregnancy (category D) and ganetespib is an agent with the potential for teratogenic or abortifacient effects. Because there is an unknown but potential risk of adverse events in nursing infants secondary to treatment of the mother with fulvestrant or ganetespib, breastfeeding should be discontinued if the mother is treated on either arm of the trial.
- 3.2.12 Individuals with the following cancers are eligible if diagnosed and definitively treated prior to study entry: cervical cancer *in situ*, basal cell or squamous cell carcinoma of the skin. Individuals with a history of other malignancy are ineligible unless disease-free for at least 3 years or deemed by the investigator to be at low risk (<10%) for recurrence of that malignancy.

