* See section 5.2 for management of diarrhea and hypersensitivity reactions. For patients who have successfully tolerated at least 2 cycles of ganetespib without a hypersensitivity reaction, routine premedication with dexamethasone and diphenhydramine prior to subsequent ganetespib infusions is not required and is left to the discretion of the treating provider.

CONFIDENTIAL

This document is confidential. Do not disclose or use except as authorized.

Patients who are randomized to Arm A may cross over to Arm C (Fulvestrant plus ganetespib) at the time of centrally confirmed progression. Patients in Arm C will start at Dose Level 1, as shown below. At the time of initial protocol design, it was decided that if the Arm B starting dose was dropped to Dose Level -1, as detailed above, then the Arm C starting dose would also be dropped to Dose Level -1. Since the DLT rule was not triggered for the first 10 patients randomized to Arm B, the Arm C starting dose has continued at Arm B Dose Level 1.

Arm C: Dose Level 1					
Agent	Pre-medications*	Dose	Route	Schedule	Cycle Length
Fulvestrant	None	500 mg	Intramuscular injection	C1: D1, C2: D1 Then on Day 1 of each subsequent cycle	28 days (4 weeks)
Ganetespib	
 • Suggest 2 mg Loperimide 1-2 hrs before infusion. • Dexamethasone 10 mg IV, or therapeutic equivalents • Diphenhydramine HCL 25-50 mg, or therapeutic equivalents (dose of diphenhydramine may be reduced per investigator discretion if patient had previous problems with 25mg or higher) 	200 mg/m ²	Intravenous (see section 5.2.1 for vascular access device restrictions)	D 1,8,15	

* See section 5.2 for management of diarrhea and hypersensitivity reactions. For patients who have successfully tolerated at least 2 cycles of ganetespib without a hypersensitivity reaction, routine premedication with dexamethasone and diphenhydramine prior to subsequent ganetespib infusions is not required and is left to the discretion of the treating provider.

CONFIDENTIAL

This document is confidential. Do not disclose or use except as authorized.

Arm C: Dose Level -1					
Agent	Pre-medications*	Dose	Route	Schedule	Cycle Length
Fulvestrant	None	500 mg	Intramuscular injection	C1: D1, \\ C2: D1 Then on Day 1 of each subsequent cycle	28 days (4 weeks)

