9.2 STUDY CALENDAR B

Arm B: Fulvestrant + Ganetespib

Note: The study calendar below describes study procedures for Arm B.

- Patients who discontinue ganetespib and/or fulvestrant for a reason other than progression should be followed at that time according to Study Calendar D.
- *Patients who are taken off Arm B for reason other than progression and who are not followed on study calendar D for any reason, should have “off-treatment” evaluation and tests as described in the “At time of progression or off-treatment” column below. Patients are then followed for survival status as described in the “follow-up” column below.

	Pre-Study	C1 D1	C1 D8	C1 D15	C2 D1	C2 D8	C2 D9	C2 D15	C3 D1	Day 1 of each cycle	D8 and D15 of each cycle (cycle 3 forward)	Every 2 cycles	At time of progression or off-treatment*	Follow-Up
Informed consent	X													
Confirm eligibility	X													
Demographics	X													
Medical History	X													
Concurrent medications	X	X	X	X	X				X	X			X	
Physical exam		X	X	X	X				X	X			X	
Vital signs ^a		X	X	X	X	X		X	X	X	X		X	
Height		X												
Weight		X	X	X	X	X		X	X	X	X		X	
ECOG perf. status	X	X	X	X	X				X	X			X	
CBC w/diff, plts	X	X	X	X	X	X		X	X	X	X		X	
Serum chemistry ^b	X	X	X	X	X	X		X	X	X	X		X	
PT, PTT ^c														
B-HCG ^d	X													
CEA, CA27-29 ^e		X							X ^e			X ^e	X	
12-lead ECG	X	X ^f			X ^f					X ^f				
Adverse event evaluation ^g	X	X	X	X	X				X	X			X	
Tumor measurements ^h	X											X ^h	X	
Bone scan ⁱ	X											X		
Fulvestrant		X		X	X				X	X				
Ganetespib		X	X	X	X	X		X	X	X	X			
Research Specimen Collection (see section 9.5)	X	X				X	X						X	
Survival Status (see Section 5.1.16)														X q3 months

CONFIDENTIAL

This document is confidential. Do not disclose or use except as authorized.

- a. Vital signs: heart rate, blood pressure, respiratory rate
- b. Serum chemistry: sodium, potassium, chloride, bicarbonate, blood urea nitrogen, creatinine, glucose (random), total bilirubin, alkaline phosphatase, ALT, AST, albumin, calcium, magnesium, phosphorus
- c. PT, PTT if clinically indicated prior to biopsy (-ies) per standard institutional guidelines
- d. In women of childbearing potential only (including premenopausal women with intact uterus and ovaries on GnRH agonist).
- e. All patients should have baseline tumor marker measurement. Tumor markers are required at other time points only when elevated at baseline.

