9.3 STUDY CALENDAR C

ARM C: Patients Assigned Arm A, After Cross-Over to Fulvestrant + Ganetespib

Note: Patients who progress on fulvestrant alone may cross over to fulvestrant + ganetespib. The first dose of ganetespib should be given only AFTER central confirmation of progression but within 2 weeks of documented progression on fulvestrant alone. Cycle number will re-set to Cycle 1 and be captured in case report forms as post-crossover treatment. Fulvestrant may be given +/- 7 days of schedule in order to allow “synchronization” of fulvestrant and ganetespib cycles.

- *Patients who are taken off Arm C for reason other than progression and who are not followed on study calendar D for any reason, should have “off-treatment” evaluation and tests as described in the “At time of progression or off-treatment” column below. Patients are then followed for survival status as described in the “follow-up” column below.

	C1 D1	C1 D8	C1 D15	C2 D1	C2 D8 and C2D15	C2 D8 and C2 D9	C3D1	Day 1 of each cycle	D8 and D15 of each cycle	Every 2 cycles	At time of progression or off-treatment*	Follow-Up
Concurrent medications	X	X	X	X			X	X			X	
Physical examination	X	X	X	X			X	X			X	
Vital signs ^a	X	X	X	X	X		X	X	X		X	
Weight	X	X	X	X	X		X	X	X			
ECOG performance status	X			X			X	X			X	
CBC w/diff, plts	X	X	X	X	X		X	X	X		X	
Serum chemistry ^b	X	X	X	X	X		X	X	X		X	
PT, PTT ^c												
CEA, CA27-29							X ^d			X ^d	X	
12-lead EKG	X ^h			X ^h				X ^h				
Adverse event evaluation ^e	X	X	X	X			X	X			X	
Tumor measurements ^f										X ^f	X	
Bone scan ^g										X ^g	X ^g	
Fulvestrant	X			X			X	X				
Ganetespib	X	X	X	X	X		X	X	X			
Research Specimen Collection (see section 9.5)											X	
Survival Status (see Section 5.1.16)												X q3 months

a. Vital signs: heart rate, blood pressure, respiratory rate

b. Serum chemistry: sodium, potassium, chloride, bicarbonate, blood urea nitrogen, creatinine, glucose (random), total bilirubin, alkaline phosphatase, ALT, AST, albumin, calcium, magnesium, phosphorus

CONFIDENTIAL

This document is confidential. Do not disclose or use except as authorized.

- c. Patients receiving ganetespib and who are on warfarin should have PT-INR checked at baseline, 1 week, 2 weeks, and 4 weeks after start of ganetespib and as clinically indicated thereafter. Patients not on warfarin are not required to have PT, PTT checked at any time, except if clinically indicated prior to a biopsy.

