- c. Patients receiving ganetespib and who are on warfarin should have PT-INR checked at baseline, 1 week, 2 weeks, and 4 weeks after start of ganetespib and as clinically indicated thereafter. Patients not on warfarin are not required to have PT, PTT checked at any time, except if clinically indicated prior to a biopsy.
- d. In women of childbearing potential only.
- e. All patients should have baseline tumor marker measurement. Tumor markers are required at other timepoints only when elevated at baseline.
- g. Baseline symptoms should be documented using the CTCAE v 4.0 grading scale. Adverse events should be documented on day 1 of each cycle, at each clinic visit, and at time of cross-over, using the CTCAE v 4.0 grading scale.
- i. Radiologic imaging studies to evaluate tumor status should be done every 2 cycles +/- 7 days. However, patients who have been on-study for >1 year are permitted to have tumor imaging performed every 2-4 cycles. Contrast computed tomography (CT) (or without contrast if contraindicated) of chest and abdomen is preferred. Magnetic resonance imaging (MRI) of chest and abdomen is an acceptable alternative. Note: PET-CT scans are not allowed per protocol for primary assessment of response. PET-CT scans may be done according to clinical judgment to supplement CT or MRI scans in cases where results of the PET-CT may clarify or resolve a clinical question. If palpable/visible lesions (e.g. chest wall nodule, etc) are being used as target lesions, measurements and photographs should be taken as well.

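### The warfarin INR schedule, worded for all patients on ganetespib, is missing from the Arm B calendar; and the entry limits are not re-applied when Arm A patients cross over to ganetespib

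*Combined protocol and SAP*

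**What the plan says.** **INR.** Section 3.1.21 admits warfarin users to either arm: "Patients on therapeutic dose anti-coagulation with warfarin, LMWH, or other anti-coagulants will be allowed to participate in the study". It has anticoagulants held around a research biopsy. It also lets a patient for whom holding is unwise enter the study without a biopsy.

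Calendar C, footnote c, says "Patients receiving ganetespib and who are on warfarin should have PT-INR checked at baseline, 1 week, 2 weeks, and 4 weeks", counted from the start of ganetespib, with later checks as indicated. Calendar D (Section 9.4) carries the same text: "Patients receiving ganetespib and who are on warfarin should have PT-INR checked at baseline". Calendar B (Section 9.2), footnote c, says only "PT, PTT if clinically indicated prior to biopsy (-ies) per standard institutional guidelines" and does not mention warfarin.

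**Crossover.** The Section 3 limits are set at entry. Section 3.1 opens "Participants must meet the following criteria on screening examination to be eligible to participate in the study" and Section 3.2 opens "Participants who exhibit any of the following conditions at screening will not be eligible for admission into the study". The limits relevant here are organ and marrow function (3.1.17), untreated or progressive brain metastases (3.2.5), pending visceral crisis (3.2.6), serious cardiac illness (3.2.9) and "Corrected QTc > 470 msec" (3.2.10).

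Section 5 then says: "Patients who are randomized to Arm A may cross over to Arm C (Fulvestrant plus ganetespib) at the time of centrally confirmed progression". Arm C starts at Dose Level 1, as Arm B does. Calendar C adds that the first dose falls within 2 weeks of documented progression. Section 5.1.12 lists laboratory tests, an ECG and performance status, but marks only the confirmation of progression as required before the first dose.

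**The concern.** Sites work from the calendar for the patient's arm. If a safety check worded for everyone on ganetespib is printed only under Calendars C and D, the larger group starting the drug, up to 47 patients in Arm B against at most 24 crossing over from Arm A, is on a calendar without it.

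The crossover question is related. Section 2.1 says that, because of the QT findings, ganetespib protocols must carry updated cardiovascular entry criteria, so those limits exist because of exposure to ganetespib. An Arm A patient is first exposed at crossover, after progression and possibly long after screening. The protocol does not say whether the limits must still be met then. Sites could handle the same result differently, and a patient outside the entry limits could start ganetespib without the protocol addressing it.

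**Working it through.** The plan gives no figure to reproduce here. The check is a comparison of texts, with simple arithmetic for scale.

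**1. Where an INR rule appears**

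| Place | Who it governs | PT/INR content |
|---|---|---|
| Calendar B, fn c | Arm B, from start of ganetespib | PT/PTT only if indicated before a biopsy |
| Sections 5.1.2 to 5.1.11 | Visits, including Arm B | None |
| Calendar C, fn c | Crossover patients | Baseline, 1, 2 and 4 weeks, if on warfarin |
| Section 5.1.12 | Time of crossover | None |
| Calendar D, fn c | After assigned therapy is discontinued | Same text as Calendar C, but no PT/PTT row in the table |

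The rule is worded for any patient receiving ganetespib, yet it is absent from the calendar under which most patients start the drug.

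**2. What pre-biopsy testing would catch in Arm B**

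- The required biopsy is at about Cycle 2 Day 9. With 28-day cycles that is study day 28 + 9 = 37, or 36 days after the first dose. The last fixed check in footnote c is at 4 × 7 = 28 days.
- Appendix B, for biopsies at one hospital, asks for PT/INR and for a recheck after warfarin has been stopped for 5 days. That recheck describes the hold, not warfarin taken together with ganetespib.
- Under 3.1.21, a patient whose anticoagulation cannot safely be held has no research biopsy, so the Calendar B trigger does not arise.

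Pre-biopsy testing therefore overlaps only partly with the schedule.

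**3. How many patients**

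The documents do not give warfarin use. Assuming 2% to 10%: 0.02 × 47 = 0.94 and 0.10 × 47 = 4.7, so about 1 to 5 Arm B patients.

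**4. Age of the eligibility results at the first ganetespib dose**

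Inputs: eligibility labs within 14 days and ECG within 28 days before randomization (Section 3); treatment within 7 days after it (Section 5).

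- Arm B, labs: at most 14 + 7 = 21 days.
- Arm B, ECG: at most 28 + 7 = 35 days.
- Crossover: no upper bound. Imaging is every 2 cycles ± 7 days, so progression at a scheduled scan is found no earlier than 2 × 28 − 7 = 49 days after treatment starts.

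Under the exponential model of Section 14.2, S(t) = exp(−ln 2 × t / median), with t = 35 / 30.4375 = 1.15 months:

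- median 4.0 months (planning value): S = 0.819, and 24 × 0.819 = 19.7, so about 20 of 24 Arm A patients are still progression-free at 35 days;
- median 3.7 months: S = 0.806;
- median 5.5 months: S = 0.865.

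The last two medians are times to progression on fulvestrant from Section 2.2. For most Arm A patients, any crossover would come later than Arm B's longest gap. Not all will cross over.

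**5. What limit attaches to the first Arm C dose**

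The results are current, because 5.1.12 repeats the ECG and labs; what is missing is a limit. After a QTc of 501 ms or more, 5.6.2 and 6.2.1 let ganetespib resume only once QTc is below 470 ms. Entry excludes QTc above 470 ms. No QTc value is attached to the first crossover dose. No hepatic, renal or brain-metastasis limit is attached to it either.

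**The case against.** **On INR.** The omission looks like a footnote not copied into Calendar B rather than a decision to treat the arms differently. The in vitro data in Section 2.1 show no significant effect of ganetespib on warfarin metabolism. A reader might infer that anticoagulation in Arm B goes unmonitored. The documents do not support that: Calendar B allows PT/PTT before a biopsy, Appendix B requires PT/INR for biopsies at one hospital, and usual care is not excluded. What stands is that the schedule tied to starting ganetespib is absent.

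A reader might also infer from the printed table that Calendar D ties this footnote to the tumor-marker row. The superscripts there are visibly garbled in the text as read from the PDF, so nothing should rest on that.

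**On crossover.** A reader might infer that the entry limits bind Arm B but not crossover patients, or that crossover has no safeguard. Neither is right. Arm A patients met every limit at entry. On the dosing day, Arm B's own labs and ECG carry no pass mark either, and the repeat-ECG response to a pre-dose QTc above 470 ms is the same in both arms. The Section 5.6 QTc rules, the ban on torsades-linked drugs, investigator discretion in Section 5.7 and the hematologic criteria to treat on the nursing sheet also apply to both. The difference that stands is elapsed time: the limits were tested once, and the protocol is silent on whether they hold when ganetespib starts after progression.

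Three further inferences go too far. That Arm B and Arm C toxicity become non-comparable: Section 14.4 describes them separately and plans no such comparison. That organ failure or brain metastases are most likely at crossover: the documents give no source. That ganetespib's poor distribution to the central nervous system adds to the risk: Section 2.1 takes this from rats and monkeys.

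**Conclusion.** The INR point holds as an internal inconsistency. A check worded for all ganetespib patients on warfarin is missing from the calendar of the 47 patients randomized to the drug, and neither Calendar D nor pre-biopsy testing fully replaces it. It probably affects few patients: about 1 to 5, on an assumed 2% to 10% warfarin use. The in vitro data lower the expected consequence.

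The crossover point holds as a secondary gap. Up to 24 patients could start ganetespib after progression with entry limits tested once, at screening, and with no stated limit on the tests collected at crossover. The estimate that about 20 of 24 would still be progression-free at 35 days rests on the planned 4.0-month exponential median.

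Neither point touches the primary analysis. Overall severity is minor to moderate.

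**What to change.** - Reconcile footnote c across Calendars B, C and D and the Section 5.1 visit lists (including 5.1.12), so that patients starting ganetespib in Arm B and in Arm C fall under one stated INR rule.
- Reconcile Section 5.1.12 and Calendar C with Section 3 and Section 5.6.2 by stating whether, and which, entry limits are re-checked on the tests already required at crossover.

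The sponsor and investigators choose the clinical rule in both cases; this review does not propose one. The cost is a text amendment, a few routine INR tests if the schedule is kept for Arm B, and possibly a few Arm A patients unable to cross over if limits are re-applied.
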